## 7.7. Concomitant Therapy

Study participants will be permitted to use concomitant medications that they require during the study, except excluded medications described in Section 6.2 (Exclusion Criteria) and Section 7.7.1 to Section 7.7.4 below. In addition, certain permitted medications (for example, treatments for blood pressure or dyslipidemia) described in Section 7.7.5 and Section 7.7.6 may be continued, but not changed, during the course of the study.

Investigative site staff will inform study participants that they must consult with the investigator or a designated site staff member upon being prescribed any new medications during the study, except when initiated for treatment of medical emergencies. Any additional medication initiated during the course of the study (including OTC drugs, such as aspirin) must be documented, and the name of the drug and the date(s) of administration must be recorded in the study participant's diary and on the "Concomitant Medications" section of the eCRF. In addition, for permitted concomitant glucose-lowering agents, the dosage will also be documented and collected.

Non-study medications taken by study participants who are screened but not randomized will not be reported to Lilly unless an SAE or AE occurs that the investigator believes may have been caused by a study procedure.

Table BDCM.4 provides a summary of criteria for use of concomitant medications that may interfere with planned assessments during the study.

**Table BDCM.4. Criteria for Use of Concomitant Medications that may Interfere with Efficacy and Safety Assessments in Study BDCM**

Drug Class	Use During Screening/Lead-In	Conditions for Use After Randomization		
		Acute therapy a	Rescue therapy	During Safety Follow-up Period
Drugs with approved weight loss indication b	Excluded	N	N/A	N
Systemic glucocorticoid therapy c	Excluded except for acute therapy a	Y	N/A	N
Antihyperglycemia medications				
GLP-1 RAs	Excluded	N	Y	Y
DPP-4 inhibitors	Permitted	N	Y	Y
SGLT2 inhibitors	Permitted	N/A	Y	Y
Insulins and insulin mixtures	Daily basal insulins Permitted. All others Excluded except for acute therapy a	Y	Y	Y
Meglitinides	Excluded	N	N	Y
Alpha-glucosidase inhibitors	Permitted	N	Y	Y
Sulfonylureas	Permitted	N	N	Y
Thiazolidinediones	Excluded	N	N	N
Metformin d	Permitted	N	Ye	Y

Abbreviations: DPP-4 = dipeptidyl peptidase-4; GLP-1 RA = glucagon-like peptide-1 receptor agonist; N = no; N/A = not applicable; SGLT2 = sodium-glucose cotransporter 2; Y = Yes.

- a Acute therapy = treatment for up to 14 days.
- b Includes Saxenda® (liraglutide 3.0 mg), Xenical® (orlistat), Meridia® (sibutramine), Sanorex® (mazindol), Adipex-P® (phentermine), Belviq® (lorcaserin), Qsymia® (phentermine/topiramate combination), Contrave® (naltrexone/bupropion) or similar other body weight loss medications including over-the-counter medications (e.g., alli® [orlistat 60 mg capsules]).
- c Does not apply to topical, intraocular, intranasal, intra-articular, or inhaled preparations;
- d Switching metformin manufacturers is allowed, as long as the dosage is the same. Changing to a metformin formulation with a different action profile (i.e., from short-acting to long-acting metformin) is not permitted.
- e For rescue therapy, metformin dose may be increased if the dose is below maximum approved dose per country-specific label.

### 7.7.1. Antihyperglycemia Medications

Insulin lispro as prandial treatment or insulin degludec are the preferred choice for rescue therapy in study participants randomized to LY3209590 or insulin degludec. The only other glucose-lowering agents allowed as rescue therapy during the study are concomitant metformin,

SLGT2 inhibitors, DPP-4 inhibitors, SU and alpha-glucosidase inhibitors. In addition, insulins other than insulin degludec may be used for short-term (up to 14 days) management of medical emergencies prior to study entry and during the study. Rescue therapy with other glucose-lowering agents, may be medically indicated in certain situations after randomization (Table BDCM.4). These situations are described in Section 7.8.2.3 (severe, persistent hyperglycemia) and in Section 8.1.1 (early discontinuation of IP).

If any new glucose-lowering medication is initiated after randomization at Visit 3, other than IP, rescue therapy, or short-term use of insulin for medical emergencies, the study participant will be required to immediately discontinue the medication and the appropriate study deviation report will be generated. Any such violation of the protocol that lasts longer than 14 days will exclude the study participant from the per-protocol (PP) population for analyses.

### **7.7.2. Concomitant Antihyperglycemia Medication**

Study participants treated with metformin in this study must be on a stable dose for at least 3 months prior to screening. The prescreening dose and formulation (short-acting or long-acting) must be maintained from the time of screening through the study participant's last visit, except as required for rescue therapy (Section 7.8.2.3).

Where appropriate, allowable OAM therapy may be obtained locally by the Lilly affiliate in the participating country from local commercial supplies and distributed to sites. It is acceptable for study participants to continue obtaining their OAM therapy by previous prescribing process. In the United States and Puerto Rico, a prescription card will be available for study participants to obtain their OAM therapy with a prescription.

Dose adjustments of allowable OAM therapy are permitted after randomization (during the treatment period) under the following circumstances:

- situations that require short-term treatment interruption in line with the product labeling for each respective country;
- situations that require dose adjustment or discontinuation per country-specific label, for example, in the case of reduced eGFR;
- in the case of increased hypoglycemia risk during the treatment period (as described in Section 7.8.2.2).

Dose reduction of allowable OAM therapy during the trial should be properly documented.

In study participants who require rescue therapy, dose increase of allowable OAM therapy is permitted, but the dose and the reason for change must be properly documented in the eCRF.

Guidance for treatment during the safety follow-up period is provided in Section 5.1.1 (Study Period 3: Safety Follow-up, Visit 801).

### **7.7.3. Medications that Promote Weight Loss**

Prescription or OTC medications that promote weight loss are exclusionary if used within the 3 months prior to screening, or any time after screening (see Section 7.7). If started after

screening, these medications should be stopped immediately. In addition, study participants should not receive an intensive diet/exercise program with the intent of reducing body weight at any time during the study, other than the lifestyle and dietary measures for diabetes treatment (see Section 6.3).

#### **7.7.4. Systemic Glucocorticoids**

Chronic systemic glucocorticoid therapy (excluding topical, intraocular, intranasal, or inhaled preparations) is exclusionary if used >14 consecutive days during the 1-month period before screening or between screening and randomization at Visit 3. Study participants who require >14 consecutive days of therapy with these medications after randomization will be excluded from the PP population for analyses.

#### **7.7.5. Antihypertensive Medications**

If used, anti-hypertensive therapy should be kept stable throughout the trial to allow assessments of the effect of randomized therapies on blood pressure.

#### **7.7.6. Dyslipidemia Medications**

If used, dyslipidemia therapy should be kept stable throughout the trial to allow assessments of the effect of randomized therapies on lipid endpoints.

### **7.8. Treatment After the End of the Study**

#### **7.8.1. Treatment After Study Completion**

Investigational Product will not be made available to study participants after conclusion of the study

Beginning on the evening of the last treatment visit (Visit 21 [Week 32] or ET visit), study participants will resume their previous basal insulin therapy. As washout of LY may take up to 10 weeks to complete, previous basal insulin therapy will be instituted using the Riddle algorithm as need based on FBG (Section 7.2.1.2.). For example, no insulin would be required until the study participant's blood glucose increases to >100 mg/dL, and then daily basal insulin would be initiated and adjusted based on weekly algorithm FBG.

#### **Study Participants treated with LY3209590:**

Study participants will receive the last injection of LY3209590 at Week 31 of the study and will switch back to their previously used basal insulin after Visit 21. Since LY3209590 has a half-life of approximately CCI of the original insulin dose and CCI of the original insulin dose. Therefore, a slow up-titration of their previously used basal insulin is necessary to prevent hypoglycemia due to overlapping insulin action. The pre-study basal insulin should be started at a dose of 10 I.U. at Visit 22 with a FBG of above 120 mg/dL for 3 consecutive days or as soon as the study participants FBG is above 180 mg/dL for 3 consecutive days. Thereafter, an

up-titration according to the modified Riddle algorithm or any country specific label should be applied.

### **Study Participants treated with Insulin Degludec:**

Study participants assigned to the insulin degludec treatment arm will switch back to their pre-study basal insulin after Visit 21. If their pre-study Basal insulin was insulin degludec they can continue with the same dose used until Visit 21 of the study. If they switch back to another basal insulin (e.g. insulin Glargine), study participants should inject a daily dose, which is 20% lower than the last dose of insulin degludec used before Visit 21 and titrate under supervision of the investigator using the country-specific label for their pre-study basal insulin.

All study participants will continue to wear a continuous blood glucose monitor during the 5-week follow-up period to ensure a safe transition back to their pre-study basal insulin.

## **7.8.2. Special Treatment Considerations**

### **7.8.2.1. Standards of Medical Care**

Investigators and other study team members are expected to treat study participants according to the nationally established standards of care for diabetes management in respective participating countries, except where that treatment would be in conflict with the protocol-provided treatment requirements. If there are no local standards of care for diabetes, the investigators should follow current published standards of care from the American Diabetes Association (2016) and the European Association for Study of Diabetes (Inzucchi et al. 2015) during their study participants' participation in this study.

This section provides guidance on management of episodes of hypoglycemic events and events of severe, persistent hyperglycemia. For effective implementation of measures described here, it is important that study participants, and their caregivers, if applicable, be well-educated about the signs and symptoms of hyperglycemia (for example, severe thirst, dry mouth, frequent micturition, or dry skin) and hypoglycemia (for example, intense hunger, sweating, tremor, restlessness, irritability, depression, headaches, disturbed sleep, or transient neurological disorders). Study participants should be instructed to contact the investigative site in the event of severe, persistent hyperglycemia or severe hypoglycemia between study visits.

### **7.8.2.2. Management of Increased Hypoglycemia Risk**

The risk associated with the allowable OAMs is low since all but the sulfonylureas are non-secretagogues; therefore, clinically relevant increases in the risk of hypoglycemia due to the OAMs are not expected in this trial. The effects of LY3209590 on hypoglycemia are not known and an objective of the study is to assess the risk of hypoglycemia in study participants receiving LY3209590.

The study uses real-time CGM to continuously monitor potential hypoglycemic events. In case of a hypoglycemic event, study participants will be proactively warned by an alarm and are instructed to immediately ingest rapidly absorbable carbohydrates. This safety measure minimizes the risk of severe hypoglycemic events during the complete study duration.

In this study, increased risk of hypoglycemia is defined as having a single episode of severe hypoglycemia or having more than 1 episode of documented symptomatic hypoglycemia within a 1-week period at any time during the treatment period.

In cases where a study participant experiences hypoglycemia as described above, to confirm the increased risk, the study sites must ensure that the study participant has been fully compliant with the assigned therapeutic regimen and also that there is no evidence of other possible causes of hypoglycemia (e.g., omission of meal, unexpected increase in exercise).

Study participants fulfilling the definition of increased risk of hypoglycemia should first decrease their OAM dose (especially SU), followed by discontinuation of OAM therapy, if needed. If the study participant continues to experience hypoglycemic events after the discontinuation of OAM therapy, the investigator should reduce the dose according to the appropriate algorithm (Section 7.2.1.2) or discontinue the study participant from IP.

#### **7.8.2.3. Management of Study Participants with Severe, Persistent Hyperglycemia during the Treatment Period**

An additional therapeutic intervention should be considered in study participants who develop severe, persistent hyperglycemia after randomization based on the following criteria (reference FDA Draft Guidance 2016):

- a) average FPG >270 mg/dL (>15.0 mmol/L) over any 2-week period or longer during the first 6 weeks postrandomization; or
- b) average FPG >240 mg/dL (>13.3 mmol/L) over any 2-week period or longer from Week 6 to Week 12 postrandomization; or
- c) average FPG >200 mg/dL (>11.1 mmol/L) over any 2-week period or longer from Week 12 to Week 18 postrandomization.

Investigators should first confirm that the study participant does not have an acute condition causing severe hyperglycemia and, after the first 12 weeks of the study, that the study participant is fully compliant with the assigned therapeutic regimen. The investigator will decide, in collaboration with the responsible clinical research physician (CRP) and in consultation with the study participant, on an appropriate glucose-lowering intervention (rescue intervention) after considering relevant clinical criteria. In general, insulin degludec will be the preferred rescue therapy for study participants assigned to LY3209590. See [Table BDCM.4](#) for allowed medications. Study participants who receive a new intervention for hyperglycemia management should also continue administering IP for the remaining period in the trial.

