### 5.1. Overall Design

Study I8H-MC-BDCM (BDCM) is a multicenter, randomized, open-label, comparator-controlled Phase 2 study with 3 study periods. A total of 536 study participants with T2DM, previously treated with basal insulin will be screened. Approximately 375 study participants will be randomized in a 1:1:1 ratio to LY3209590 in one of two dosing algorithms ([Appendix 7](#)) or insulin degludec (modified Riddle algorithm, [Section 7.2.1.2](#)). The study is designed to evaluate the efficacy and safety of LY3209590 compared with insulin degludec.

The study will consist of 3 periods: 2-week screening, 32-week treatment period, and 5-week safety follow-up period.

Study governance considerations are described in detail in [Appendix 3](#).

[Figure BDCM.2](#) illustrates the study design.

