### **General considerations**

Study procedures will be performed as listed in the Schedule of Activities (Section [2](#)).

In order to allow timely sampling for PK assessments, visits for collection of the samples will be scheduled within the required time windows provided in the Schedule of Activities (Section [2](#)).

Study participants will continue to use concomitant OAMs throughout the treatment period: discontinuation or changes to dose are not permitted, except in situations where dose adjustment or complete discontinuation is required per country-specific label or when allowed per study protocol (for further details see Section [7.7.2](#)).

Study participants will be instructed to document fasting plasma glucose (FPG) each day by using the values displayed on their CGM device after waking or using a finger-stick glucose measurement. In addition, two 6-point SMPG profiles (prior to and 2 hours after the morning, midday, and evening meals) should be documented on non-consecutive days in the week prior to the required visits noted in the Schedule of Activities using CGM-based glucose values, (Section [2](#)).

Study participants who develop severe, persistent hyperglycemia based on prespecified thresholds (see Section [7.8.2.3](#)) will receive a new glucose-lowering intervention (or rescue therapy) based on clinical judgment of the investigator (see [Table BDCM.4](#)). Study participants who need rescue therapy will continue on IP in the trial until they complete all study visits.

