#### **7.2.1.2. Insulin Degludec**

Insulin degludec will be initiated at the same dose as the total daily basal insulin dose already administered, or in accordance with the locally approved product labeling if different.

Thereafter, a dosing algorithm adapted from Riddle et al. 2003 will be used by investigators for adjusting insulin degludec to target an FBG  $\leq 100$  mg/dL ( $< 5.6$  mmol/L) in order for study participants to achieve glycemic goals of an HbA1c value  $< 7.0\%$  and a pre-prandial capillary plasma glucose (PG) between 71 and 130 mg/dL (3.9 to 7.2 mmol/L; ADA 2011). In situations where study participant safety is a concern or where dose adjustments have not had the desired therapeutic effect, investigators may only make increased adjustments to the dose of insulin degludec recommended by the dose-adjustment algorithm after consultation with Lilly.

At the time of site visit or telephone visit, the investigator will assess the study participant's glycemic control for the previous week and, if necessary, inform the study participant about any needed dose adjustment. The dose will be based on the study participant's blood glucose value. Adherence to the dosing algorithm provided for this study is required from Visit 3 (randomization) up to Visit 21 (Week 32, inclusive) and will be monitored periodically by the study team. Dose increases may be made at weekly intervals and no sooner than 5 days following the last dose increase. In some cases, study participant visits could occur sooner than 5 days apart due to the allowable visit window; however, there should be no dose increase if at least 5 days have not elapsed since the previous dose increase. In contrast, the insulin degludec dose may be reduced at any time on the judgment of the investigator. Any deviations from this guidance must be approved by Lilly.

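### The numeric rescue criteria stop at Week 18 of a 32-week treatment period, leaving the status of a late add-on glucose-lowering agent ambiguous; separately, Section 8.2 contradicts the rescue rules at any week

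*Protocol*

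**What the plan says.** Protocol Section 5.1 describes a "2-week screening, 32-week treatment period, and 5-week safety follow-up period". Section 7.8.2.3 lists three fasting plasma glucose (FPG) criteria, each an average over at least two weeks: above 270 mg/dL in the first 6 weeks, above 240 mg/dL from Week 6 to Week 12, and finally "average FPG >200 mg/dL (>11.1 mmol/L) over any 2-week period or longer from Week 12 to Week 18 postrandomization". The list is unredacted and ends there. The SAP gives no threshold or rescue definition of its own.

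Other sections rely on this list:

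- Section 5.1.1 gives rescue to "Study participants who develop severe, persistent hyperglycemia based on prespecified thresholds", citing Section 7.8.2.3, and adds: "Study participants who need rescue therapy will continue on IP in the trial until they complete all study visits".
- Section 7.7.1 says of the situations that may call for rescue: "These situations are described in Section 7.8.2.3 (severe, persistent hyperglycemia) and in Section 8.1.1 (early discontinuation of IP)". It then sets the default for everything else. "If any new glucose-lowering medication is initiated after randomization at Visit 3, other than IP, rescue therapy, or short-term use of insulin for medical emergencies", then "the study participant will be required to immediately discontinue the medication and the appropriate study deviation report will be generated".
- SAP Section 4.1 removes from the efficacy analysis set (EAS) all data after rescue medication, acute therapy excepted. SAP Section 4.7 runs the primary Week 32 HbA1c analysis on the EAS.
- Protocol Section 8.2, under investigator decision, has the participant leave the study before any other agent effective for the indication is introduced. It makes no exception for rescue.

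**The concern.** The thresholds tighten from 270 to 240 to 200 mg/dL and then end, just as the trial enters the stretch leading to the primary endpoint. Consider a participant on IP whose two-week average FPG is above 200 mg/dL. In Week 16 a rescue criterion is met. In Week 22 none is.

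If a new agent is then started for longer than an acute course while IP continues, its label decides what happens to the Week 32 HbA1c. Those applying the label know the treatment arm. Explicit triggers keep such decisions uniform across arms and sites, and they tell the investigator when a participant's hyperglycemia warrants action.

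The Section 8.2 conflict is a separate matter, unrelated to the Week 18 bound. Followed as written at any week, it would take a participant who needs rescue out of the study and lose the later HbA1c for the sensitivity analysis too.

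**Working it through.** **Coverage.** Inputs: treatment period 32 weeks (Section 5.1); last criterion ends at Week 18 (Section 7.8.2.3).

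- Weeks without a numeric criterion: 32 − 18 = 14; 14/32 = 43.75%.
- Scheduled contacts after randomization (Schedule of Activities): Weeks 1 to 12 (12 contacts), then 15, 18, 21, 24, 28 and 32, so 12 + 6 = 18. Four of the 18 fall after Week 18.

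These are shares of calendar time and contacts. They are not shares of participants or events.

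**One late case, read under each rule.** A rescue-eligible agent is started in Week 22 for persistent hyperglycemia, used beyond 14 days, with IP continuing.

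- *As rescue* (Table BDCM.4 plus investigator and sponsor-physician judgment): IP continues, and later HbA1c, including Week 32, leaves the EAS.
- *As a deviation* (Section 7.7.1 read literally, since no Section 7.8.2.3 criterion is met): the agent must be stopped and reported. The EAS rule does not remove the HbA1c. Use beyond 14 days excludes the participant from a per-protocol population, which the SAP does not define.
- *Under Section 8.2*: the participant leaves the study before the agent starts. This would apply equally in Week 10.

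Two neighboring cases are already settled. Emergencies are allowed up to two weeks in total before Visit 21 (Section 7.8.2.4), and a new agent is permitted after IP is stopped for good (Section 8.1.1).

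**Cost of the fix in precision.** Inputs from Section 10.1: SD 1.1, margin 0.4, true difference 0, two-sided alpha 0.1, 200 pooled LY3209590 completers against 100 on degludec.

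- SE = 1.1 × √(1/200 + 1/100) = 0.135. Noncentral t power with 298 df = 0.906, which reproduces the stated 90%.
- The documents give no rescue rate, so the share of completers per arm losing the Week 32 value is an assumption. With loss p, SE becomes 0.135/√(1 − p):
  - 2%: SE 0.136, power 0.901
  - 5%: SE 0.138, power 0.893
  - 10%: SE 0.142, power 0.878
  - 15%: SE 0.146, power 0.861

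These are complete-case figures. The planned repeated-measures model also uses earlier visits. They price the fix only. The effect of the gap itself on the primary estimate cannot be computed from the documents.

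**The case against.** The strongest reply is that only a number is missing.

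- The Section 7.8.2.3 thresholds are prompts at any week: intervention is to be considered, and the investigator decides with the sponsor's physician on clinical grounds.
- Table BDCM.4 sorts agents into acute and rescue use with no week limit and caps acute use at 14 days. EAS censoring turns on rescue as opposed to acute medication, and does not ask whether a threshold was met. A longer course of a rescue-eligible agent in Week 22 can fit that wording.
- Titration continues: "Adherence to the dosing algorithm provided for this study is required from Visit 3 (randomization) up to Visit 21 (Week 32, inclusive)". Sections 7.2.1.1 and 7.2.1.2 and Appendix 7 allow off-algorithm dosing after sponsor consultation when the effect is inadequate. Degludec rises by 8 U when the algorithm value exceeds 180 mg/dL. None of this ends at Week 18.
- SAP Section 4.8 includes a treatment-policy analysis that keeps endpoint data regardless of treatment disposition.

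All of this stands, and it makes the open case narrow. It does not close it. Sections 5.1.1 and 7.7.1 still tie on-IP rescue to a list that ends at Week 18, so the literal reading points to a deviation while Table BDCM.4 allows rescue. The sensitivity analysis targets a different estimand and does not make EAS censoring consistent.

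A reader might infer that nothing governs rescue after Week 18, that late HbA1c stays in the EAS by default, or that the primary result is biased. The documents do not support these readings: judgment, drug class and the acute-therapy limit still operate; keeping the HbA1c is one reading among several; and no rescue rate or imbalance between arms is given.

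**Conclusion.** The point holds as a minor one. The FPG criteria leave 14 of 32 weeks without a numeric rescue trigger for participants on IP. In that period the status of a late, non-acute add-on agent is ambiguous between rescue and deviation, with opposite consequences for the Week 32 value in the EAS. For the gap to matter, algorithm titration must fail, off-algorithm escalation must fail or not be used, IP must continue, and a non-acute agent must be added. How often that happens is unknown.

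The contradiction between Section 8.2 and Sections 5.1.1 and 7.8.2.3 is definite and independent of the week. The coverage figures rest only on the stated week ranges; the precision figures rest on assumed losses.

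**What to change.** 1. In Section 7.8.2.3, change criterion (c) to run from Week 12 through Week 32.
2. In the Section 8.2 rule on another effective agent, add: *other than rescue therapy under Section 7.8.2.3*.
3. In the SAP, state that any non-acute (more than 14 days) glucose-lowering agent started for persistent hyperglycemia while on IP counts as rescue for EAS censoring, whether or not a threshold was met.

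Item 3 alone settles the analysis question. Item 1 gives participants in Weeks 18 to 32 the same explicit trigger as in Weeks 12 to 18, and item 2 removes the conflict. The cost is two wording changes in a short protocol amendment and one SAP sentence, with no new data. The downside is that a few more post-rescue values may leave the EAS: on the assumed losses above, power would fall from 0.91 to between 0.90 (2% lost) and 0.86 (15% lost). Some clinical judgment about rescue will remain, as it does before Week 18.
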